7.4. Safety Objectives and Endpoints

Safety		Safety Endpoints	
Objective	Parameter Description	Parameter Formula	Abbreviated Description
Characterize the safety of PD G 506 A	Rate of procedure- related WHO grade 3-5 adverse events.	P(S.1) = # of procedure related AEs (WHO grade ≥3)	Safety of the procedure.
and the Eagle V1.2 Imaging System in patients undergoing fluorescence imaging during breast cancer surgery (Arm 1 and	Rate of drug-related WHO grade 3-5 adverse events.	$P(S.2) = \#$ of drug related AEs (WHO grade ≥ 3)	Safety of the drug.
Arm 2).	Rate of device-related WHO grade 3-5 adverse events.	$P(S.3) = \#$ of device related AEs (WHO grade ≥ 3)	Safety of the device.

Safety assessments will include:

- Adverse events
- Serious adverse events
- Blood analysis: complete blood count, aspartate aminotransferase, alanine transaminase, total bilirubin level, creatinine

	SBI-CIP 20-002	Rev: v1.8	A prospective multi-center clinical study evaluating the use of PD G 506 A and the Eagle V1.2 Imaging System for the visualization of carcinoma during breast conserving surgery	Page: 45 of 157
--	-----------------------	--------------	--	-----------------

8. Study Design

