Only data from participants in Part B will be used for the analyses of primary and secondary efficacy. Data from all participants in both Part A and Part B will be used for the evaluation of safety.

In Part B of the study, participants will be randomized in a ratio of 1:6 (Arm 1 [SoC]: Arm 2 [PD G 506 A]).

The randomization will be stratified by breast cancer type (invasive carcinoma with or without in situ carcinoma vs. in situ carcinoma alone). This will ensure an approximate ratio of 1:6 within each type of breast cancer. Preoperative diagnosis based on diagnostic tissue sampling performed during screening (e.g. percutaneous core needle biopsy, fine-needle aspiration cytology) will be

SBI-CIP 20-002 Rev: v1.8 A prospective multi-center clinical study evaluating the use of PD G 506 A and the Eagle V1.2 Imaging System for the visualization of carcinoma during breast conserving surgery	Page: 46 of 157
---	-----------------

used for stratification. Permuted blocks will be used to construct the randomization schedule and the randomization will be implemented using an interactive web response system.

Data from the SoC arm (Arm 1) will not be used for statistical analysis of the primary and most secondary endpoints. The purpose of the SoC arm is to compare resected tissue weight, patient reported cosmetic outcomes, re-excision prior to initiation of adjuvant therapies, re-excision within 1-year of index BCS, and safety between study arms as well as to minimize bias introduced into the SoC procedure if the *surgeon* is aware that they have an opportunity to revise the margins further after SoC is complete. A 3-month, 6-month and 1-year follow-up will be performed to evaluate patient reported cosmetic outcomes as well as the rate of re-excision across both study arms. The 6-month and 1-year follow-up data will be collected as an extension phase to the study, meaning database lock and analysis of all other endpoints will be performed following the last patient's 3-month follow-up data is collected. Analysis of 6-month and 1-year data will occur after the last patients 1-year visit. The clinical study report will be appended to include the 6-month and 1-year data, when available.

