10.3. Blinding

Part A of the study is not blinded as all participants will receive PD G 506 A. Although surgeons will not be blinded to treatment in Part A, they will follow all of the same procedures as in Part B and will not perform any fluorescence assessments until SoC resection is complete. In the main study, Part B, the participants and pathologist(s) (and pathologist's assistant) will be blinded to the treatment assignment for the duration of the trial. The *surgeon* and *surgeon's assistant* will be blinded to the treatment assignment up until the time that the SoC lumpectomy procedure is complete, at which point they will be unblinded. The *surgeon* will also be blinded to the fluorescence imaging data collected by the *surgeon's assistant* during SoC (e.g. imaging data of the, *primary specimen* and *SoC-driven cavity shaves*) until such time that they are intentionally unblinded per protocol.

At clinical sites where specimen biopsies are collected from inside the sectioned specimen, the individual grossing the specimen (e.g. pathologist's assistant) will remain blind to the fluorescence imaging data collected by the *surgeon* or *surgeon's assistant*.

In order to maintain this blind, an otherwise uninvolved 3rd party (e.g. pharmacist) will be responsible for the reconstitution and dispensation of the study drug and dispensation of the placebo (drinking water) and will endeavor to ensure that there are no differences in time taken to dispense following randomization. The investigational drug or placebo will be administered by a blinded qualified medical professional (e.g. nurse). Neither the *surgeon* nor *surgeon's assistant* can administer the study drug due to the potential risk that the patient's reaction to consuming the investigational product accidentally unblinds the individual dosing them.

The sponsor must be notified before the blind is broken unless identification of the study treatment is required for a medical emergency in which the knowledge of the specific blinded study treatment

SBI-CIP 20-002 Rev: v1.8 A prospective multi-center clinical study evaluating the use of PD G 506 A and the Eagle V1.2 Imaging System for the visualization of carcinoma during breast conserving surgery Page: 59 of 157	
--	--

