13.2. Classification of an Adverse Event

13.2.1. Severity of Event

All AEs will be assessed by the PI using the protocol defined grading system. The Common Terminology Criteria for Adverse Events (CTCAE) Version 5.0 published by the U.S. Department of Health and Human Services (November 27, 2019)⁶⁹ will be used to grade the severity of AEs.

For AEs not included in the CTCAE defined grading system, the following guidelines will be used to describe severity⁶⁹:

- **Grade 1, Mild;** asymptomatic or mild symptoms; clinical or diagnostic observations only; intervention not indicated.
- Grade 2, Moderate; minimal, local or non-invasive intervention indicated; limiting age-appropriate instrumental activities of daily life (ADL)*.
- Grade 3, Severe or medically significant but not immediately life-threatening; hospitalization or prolongation of hospitalization indicated; disabling; limiting self-care ADL**.
- Grade 4, Life-threatening consequence; urgent intervention indicated.
- Grade 5, Death related to AE.
- *Instrumental ADL refers to preparing meals, shopping for groceries or clothes, using the telephone, managing money, etc.
- **Self-care ADL refers to bathing, dressing and undressing, feeding self, using the toilet, taking medications, and not bedridden.

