15.8. Safety Analysis

The safety of the procedure and device will be assessed for both Arm 1 and Arm 2. The rates of procedure-related WHO grade 3-5 adverse events, drug-related WHO grade 3-5 adverse events, and device-related WHO grade 3-5 adverse events will be summarized descriptively by treatment arm. Additional summaries may be performed. Full details will be provided in the SAP.

16. Data Management

Data management will be performed according to the Data Management Plan to ensure the accuracy, quality and integrity of the data.

eCRFs will be used to capture study assessments and data. The study coordinator or other delegated study staff will enter data from source documents into the eCRFs. Training will be provided for the electronic data capture (EDC) system. All study staff using the EDC system must have the necessary education, training, and experience or any combination of these. The investigator will be responsible for documenting employee education, training, and previous experience that pertain to the EDC system for all site staff using the EDC system. The investigator must maintain adequate security of the EDC system, including documentation that all users have been trained and a list of authorized users. To ensure all data entries can be tracked, all personnel responsible for data entry

|--|

must obtain a unique user identification (user ID) and password before any data can be entered in the eCRFs. Authorized study staff will be assigned a unique user ID only after receiving training.

The investigator must make study data accessible to the site monitor, other authorized representatives of the sponsor, and the appropriate regulatory authority inspectors. The eCRF for each subject will be checked against source documents at the site by the site monitor, and a final copy of the eCRF will be signed by the investigator with an electronic signature. A copy of the final eCRFs will be provided to the investigator in PDF after study closure to be kept in the investigator's study files. See the Data Management Plan for additional details.

17. Deviation from the Clinical Investigation Plan

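### The safety endpoints P(S.1)–P(S.3) are called rates but written as event counts without a denominator, and their WHO grade threshold does not match the CTCAE v5.0 grading used for adverse events

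*Combined protocol and SAP*

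**What the plan says.** Section 7.4 lists three safety endpoints: procedure-, drug- and device-related. The description column calls each a rate, for instance "Rate of drug-related WHO grade 3-5 adverse events". The formula column gives only a number of events: "of procedure related AEs (WHO grade ≥3" for P(S.1) and "of device related AEs (WHO grade ≥ 3" for P(S.3), with P(S.2) in the same form. None has a denominator or a multiplication by 100%.

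Section 13.2.1 sets the severity scale. CTCAE v5.0 "will be used to grade the severity of AEs". For terms outside it there is a generic 1-to-5 scheme: "For AEs not included in the CTCAE defined grading system, the following guidelines will be used to describe severity". No WHO scale is defined.

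Section 15.8 again speaks of rates of WHO grade 3–5 events, which "will be summarized descriptively by treatment arm", and leaves full details to the SAP. It names neither the unit (patients or events) nor the denominator.

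Section 8.1 says that "participants will be randomized in a ratio of 1:6" (Arm 1 to Arm 2) and names comparison of safety between arms as one purpose of Arm 1. Under Section 10.3 the surgeon and assistant are blinded until the standard-of-care lumpectomy is complete, "at which point they will be unblinded".

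**The concern.** A formal endpoint should fix what is counted, over whom, and on which scale. Here the description and the formula disagree on the first two, and the threshold disagrees with the severity section on the third. Whoever programs the tables would have to choose between events and patients, choose the denominator, and decide that a WHO grade means a CTCAE grade. A count of events also lets one patient with several events weigh several times.

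The restriction to related events matters because safety is meant to be compared between arms. Section 13.2.3 has the investigator judge causality. At Week 2 (Section 12.7) the surgeon, who by then knows the arm, asks about and records adverse events. An event in a patient known to have received water is unlikely to be called drug-related.

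What is at stake is a clear safety table and a usable comparison with the placebo arm. No error rate or sample size is involved.

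**Working it through.** **1. Arm sizes.** Section 15.2 states 72 and 428, 500 in all, and 525 with 5% loss. These reproduce. For a one-sample Z test with null variance, p0 = 0.01, p1 = 0.03, two-sided α = 0.05 and 90% power:

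n = [1.960·√(0.01·0.99) + 1.282·√(0.03·0.97)]² / 0.02² = 427.7, so 428 in Arm 2.

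428 × 7/6 = 499.3, so 500 in total; 500 × 1.05 = 525.

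**2. Literal reading of the formula.** If the mean number of qualifying events per patient is m in both arms, expected counts are 72m and 428m, and their ratio is 428/72 = 5.94 whatever m is. At 525 patients it is 450/75 = 6.0. If about 75 Part A patients are added to the exposed side it is (428 + 75)/72 = 6.99. The documents give no event frequency, so m below is an assumption shown over a range.

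| Assumed m | Arm 1 | Arm 2 | Ratio |
|---|---|---|---|
| 1% | 0.72 | 4.28 | 5.94 |
| 2% | 1.44 | 8.56 | 5.94 |
| 5% | 3.6 | 21.4 | 5.94 |
| 10% | 7.2 | 42.8 | 5.94 |

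With any per-patient denominator the ratio under equal frequency is 1.0.

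**3. Where equal frequency is plausible.** It is a reasonable starting point for P(S.1). It is not for P(S.2), because Arm 1 receives no drug. Nor is it for P(S.3): under Section 12.4.3 Arm 1 has imaging of excised specimens only, with none of the cavity.

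**4. Is the missing denominator a reading artefact?** Probably not. All three formulas share the form, while the proportion endpoints in Sections 7.1 and 7.2 carry a denominator and 100%.

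**5. Which denominator?** Section 15.4.2 defines a safety population for all safety analyses but limits it to randomised subjects, with receipt of study drug required in Arm 2 only. Part A is not randomised (Section 8.1), yet Sections 8.1 and 15.2 include Part A in safety, and 15.2 wants Part A, Part B and both together. The named population therefore does not cover everyone who is to be analysed.

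**6. What 72 controls can show.** With no events in 72 patients, the exact two-sided 95% upper limit is 1 − 0.025^(1/72) = 5.0%. For a risk difference with the same true risk p in both arms, the approximate 95% half-width is 1.96·√[p(1−p)(1/72 + 1/428)]. This gives 5.4 percentage points at p = 5% and 7.5 points at p = 10% (both assumed).

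**The case against.** The strongest reply is that the intent is clear enough. Sections 7.4 and 15.8 both say rate, Section 15.1 promises counts and proportions for categorical variables, and Section 15.4.2 names an analysis set. The summary has no test, threshold or decision rule. Section 15.8 defers detail to the SAP, and no separate SAP text stands in the document reviewed. All of this stands. It makes a literal count unlikely in practice and removes any inferential consequence. It does not settle the unit, the Part A denominator or the scale, which the protocol states in conflicting ways.

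Three stronger readings are tempting and are not supported.

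- A reader might infer that the drug arm will be reported with a spurious six-fold excess. That needs the formula applied literally and equal frequency in both arms, which does not fit drug- or device-related events.
- A reader might infer that the grade needed is not recorded. Section 13.2.1 grades all adverse events on a 1-to-5 scale, so grade 3–5 is available; the label is what is wrong.
- A reader might infer that the placebo arm has lost its value for safety, or that the drug comparison is empty. Section 13.4.1.1 requires all adverse events to be documented whatever their relationship, and Section 7.4 also lists adverse events, serious adverse events and blood tests. Dosing is 2 to 4 hours before anaesthesia and is given by blinded staff (Section 12.4.1), so acute reactions arise, and can be attributed, while the surgical team is blinded. Participants stay blinded throughout, and Section 13.2.3 has the pharmacovigilance vendor review relatedness. The attribution problem is confined to events judged after unblinding, which fluorescence-guided resection makes unavoidable.

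**Conclusion.** The point holds as an inconsistency in stated endpoint definitions that should be corrected. P(S.1)–P(S.3) are named as rates, written as counts without a denominator, and tied to a WHO grade that the severity section does not use. Taken literally, allocation alone would give a count ratio of about 5.9, on the assumption of equal per-patient frequency, which is most relevant to P(S.1). A rate is probably meant, and type I error, power and sample size are untouched.

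Separately, because all three endpoints keep only related events and some attributions will be made with the arm known, they are a limited basis for the between-arm safety comparison that Section 8.1 sets as a purpose of Arm 1. This applies most to P(S.2). How limited depends on the share of events attributed after unblinding, which the documents do not give.

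**What to change.** In Sections 7.4 and 15.8:

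- Define each endpoint as the number of patients with at least one related CTCAE v5.0 grade ≥3 event, divided by treated patients in that arm, × 100%. Event counts may be shown alongside.
- Replace the WHO label with CTCAE v5.0, including the Section 13.2.1 fallback for unlisted terms.
- Give denominators for Part A, Part B by arm, and the two parts pooled. Reconcile Section 15.4.2 with Sections 8.1 and 15.2 on Part A, and state what counts as treated in Arm 1, since 15.4.2 requires dosing only in Arm 2.

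For the Part B arm comparison, add the number and percentage of patients with any grade ≥3 adverse event regardless of attribution, with the risk difference and its 95% interval.

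The cost is wording and one table; no new data, visits or patients are needed. The interval will be wide because Arm 1 has only about 72 patients, and the report should say so.

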8.1. Description of the Study Design

This pivotal study is a 2-part, double -blind (pathologist(s) & patient – blinded) randomized placebo-controlled trial (Arm 1: placebo + SoC BCS, Arm 2: SoC BCS + Eagle V1.2 Imaging System + PD G 506 A) to evaluate the *patient-level* clinical usefulness, as well as *patient-* and *orientation-level* diagnostic performance and safety of PD G 506 A-induced fluorescence for the real-time visualization of carcinoma missed by SoC lumpectomy for breast cancer. Part A is an open-label training phase of the study to optimize workflow and train *surgeon's* and *surgeon's* assistant on the day 1 study-specific procedures; Part B of the study is randomized and double -blind and will serve as the pivotal portion of the study. The Eagle V1.2 Imaging System will be used for the visualization of fluorescence. SBI ALApharma Canada requires completion of the Investigator Training Program to ensure the controlled distribution and safe use of PD G 506 A investigational drug and the Eagle V1.2 Imaging System investigational medical device to trained surgeons for use in clinical trials.

Part A will not be randomized; all participants in Part A will receive PD G 506 A. The Day 1 procedures for Part A patients will be carried out with support and oversight from the Sponsor. Part A will include approximately 75 patients. Data acquired from the first 30 patients in Part A will be used to optimize the study workflow and to confirm the sample size for Part B. The remaining approximately 45 patients on Part A will be allocated to training for *surgeon's* and *surgeon's* assistants prior to their enrolling patients into Part B. All *surgeon's* and *surgeon's* assistants must complete at least 1 procedure in Part A, before enrolling a patient into Part B. A given site can only be enrolling patients for either Part A or Part B at any given time. In the event a new *surgeon* is brought onto the study after the site has begun enrolling patients into Part B, they must shadow a study surgeon for at least one Arm 2 patient procedure. In the event a new *surgeon's assistant* is brought onto the study after the site has begun enrolling patients into Part B, they must shadow a study surgeon assistant for at least one patient procedure before participating in as the *surgeon's assistant*.

Only data from participants in Part B will be used for the analyses of primary and secondary efficacy. Data from all participants in both Part A and Part B will be used for the evaluation of safety.

In Part B of the study, participants will be randomized in a ratio of 1:6 (Arm 1 [SoC]: Arm 2 [PD G 506 A]).

The randomization will be stratified by breast cancer type (invasive carcinoma with or without in situ carcinoma vs. in situ carcinoma alone). This will ensure an approximate ratio of 1:6 within each type of breast cancer. Preoperative diagnosis based on diagnostic tissue sampling performed during screening (e.g. percutaneous core needle biopsy, fine-needle aspiration cytology) will be

SBI-CIP 20-002 Rev: v1.8 A prospective multi-center clinical study evaluating the use of PD G 506 A and the Eagle V1.2 Imaging System for the visualization of carcinoma during breast conserving surgery	Page: 46 of 157
---	-----------------

used for stratification. Permuted blocks will be used to construct the randomization schedule and the randomization will be implemented using an interactive web response system.

Data from the SoC arm (Arm 1) will not be used for statistical analysis of the primary and most secondary endpoints. The purpose of the SoC arm is to compare resected tissue weight, patient reported cosmetic outcomes, re-excision prior to initiation of adjuvant therapies, re-excision within 1-year of index BCS, and safety between study arms as well as to minimize bias introduced into the SoC procedure if the *surgeon* is aware that they have an opportunity to revise the margins further after SoC is complete. A 3-month, 6-month and 1-year follow-up will be performed to evaluate patient reported cosmetic outcomes as well as the rate of re-excision across both study arms. The 6-month and 1-year follow-up data will be collected as an extension phase to the study, meaning database lock and analysis of all other endpoints will be performed following the last patient's 3-month follow-up data is collected. Analysis of 6-month and 1-year data will occur after the last patients 1-year visit. The clinical study report will be appended to include the 6-month and 1-year data, when available.

8.2. Patient and Study Completion

A study patient is considered to have completed the study if she has completed all phases of the study, including the post-operative follow-up visit (10 -14 days after their surgical procedure), and data through the 1-year follow-up has been retrieved and recorded. A study site will be closed only after all follow-up data through 1-year are collected on all patients from that site.

For analyses of Primary and Secondary efficacy endpoints, the end of the study is defined by the receipt of the 3-month follow-up data from the last patient in the study. The end of the extension phase of the study is defined as the date the 1-year follow-up data is retrieved and recorded for the last participant in the study.

8.3. Minimizing Bias

The following precautions are in place to minimize bias in data collection:

- No personnel involved with the surgical procedure (i.e., *surgeon*, *surgeon's assistant*) will be aware of the participant's randomized treatment assignment nor be present when the participant is provided with the study drug to ingest.
 - o Blinded research personnel will be instructed not to solicit any information from the participant regarding the taste and/or smell of the investigational drug.
- The participant will be blinded to whether they have been randomized to Arm 1 or Arm 2 for the duration of the study.
- The *surgeon* will be blinded to whether a participant has been randomized to Arm 1 or Arm 2 until the time at which the *surgeon* declares the SoC lumpectomy is complete.
- The individual (e.g. pathologist's assistant, pathologist) processing the surgical specimen(s) will be blind to the manner (e.g. SoC vs. *FGR*) by which samples are obtained and the FL status of the samples. This individual will also be blind to the fluorescence

SBI-CIP 20-002 Rev: v1.8 A prospective multi-center clinical study evaluating the use of PD G 506 A and the Eagle V1.2 Imaging System for the visualization of carcinoma during breast conserving surgery	Page: 47 of 157
---	-----------------

- imaging data collected of the bisected/serially sectioned primary specimen during the perioperative procedures.
- The pathologist performing the histopathological evaluation will be blind to the manner (e.g. SoC vs. *FGR*) by which the samples are obtained and the FL status of the samples.
- To ensure FL-imaging does not influence **SoC margin assessment**, intraoperative data collection tools will document the completion of SoC prior to the **surgeon** being given access to any previously acquired FL imaging data and performing additional FL imaging.

